#### **4.5 MULTIPLE COMPARISONS**

Multiplicity for the primary and key secondary endpoints will be managed through a series of hypotheses presented in Section 6.2.

#### **4.6 DATA DERIVATIONS AND TRANSFORMATIONS**

The baseline value for a variable is defined as the last non-missing value for the variable prior to or at randomization/ (day of implant), unless otherwise specified.

### **5 STUDY SUBJECTS**

At least 350 subjects who meet all inclusion/exclusion criteria will be randomized in the study across multiple investigative sites.

#### **5.1 DISPOSITION OF SUBJECTS**

Frequency counts and percentages of all subjects who are randomized and experience one of the following will be presented for each treatment group using the ITT analysis set:

- Conduit abandonment
- Death

For all subjects who discontinue from the study (or are censored), the reason for discontinuation will be reported by treatment group.

A subject listing for early discontinuations and reasons for discontinuation will be provided for the ITT analysis set.

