### 3 INVESTIGATIONAL PLAN

#### 3.1 STUDY DESIGN

This is a prospective, multicenter, multinational, open-label, randomized, two-arm, comparative phase 3 study. Approximately 35 sites in the US, Europe and Israel are planned for the study. Subjects who continue to meet inclusion and exclusion criteria on the day of surgery will be randomized in a 1:1 ratio to receive either the HAV or the ePTFE graft during surgery. The randomization will use a block size of 4 subjects and will be stratified by the upper arm or forearm placement. Subjects are considered enrolled at the time of completed informed consent. At least 350 subjects with implanted study conduits [175 with Human Acellular Vessel (HAV), 175 with an expanded polytetrafluoroethylene graft (ePTFE)] are planned to be enrolled in the study.

All enrolled subjects will be followed by study specific visits until the subject completes 2 years (24 months) of follow-up after implantation (irrespective of patency status).

After 2 years, only subjects with a patent conduit will continue to be followed (while the study conduit remains patent) for up to 5 years (60 months) post-implantation or until conduit abandonment (loss of Secondary Patency) at routine study visits. The expected duration of the clinical investigation is 76 months from the initiation of enrollment through the completion of data collection. See Appendix 1 of the study protocol for details of the schedule assessments.

A Data Monitoring Committee (DMC) will be established to review safety on an ongoing basis and to provide recommendations about stopping, continuing or otherwise modifying the study. The DMC will review data unblinded by treatment group and will consist of individuals who are not directly involved in the conduct of the study. As part of their oversight of study conduct, the DMC will review the pattern of interventions and abandonments between treatment groups overall and by study site to assess whether the management of access complications is similar in the two treatment groups.

A separate charter will be established that will describe the roles and responsibilities of the DMC. Responsibilities of the DMC will include review of aggregate safety data from other studies in the HAV clinical development program.

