## 6 EFFICACY ANALYSIS

### 6.1 PRIMARY EFFICACY ENDPOINT AND ANALYSIS

The primary efficacy endpoint is the time to loss of Secondary Patency assessed when all patients are at least 18 months after implantation (or have been censored). The primary analysis will be non-inferiority analysis using the following censoring rules:

- Subjects who have patent study conduits at the time of death, kidney transplant, voluntary withdrawal will be censored at that timepoint
- Subjects who are lost to follow-up will be censored at their last visit when it was known that the study conduit was patent
- Subjects who are lost to follow up and whose study conduit was not patent at the last completed visit will be treated as abandoned at the time of study conduit occlusion
- Subjects in whom a delayed decision is made to abandon the study conduit (e.g. delayed and then failed thrombectomy) will have the date of abandonment set as the date of the initial recognition of the thrombosis, not the date that a final decision is made
- For subjects who discontinue early or who complete without meeting criteria for the event, the time-to-event will be censored and defined as the number of days from randomization to the subject's last visit during the study

These censoring rules will apply to all 'time to' analyses. Subjects with End Stage Renal Disease (ESRD) have significant co-morbidities, with an annual death rate of ~20% (USRDS). Given the nature of the investigational product and the clinical setting, it is unlikely that the investigational product will be a causative factor in the overall death rate, and it is likely that the non-product related death rate will be similar in the two arms. For this reason, the primary analysis of Primary and Secondary Patency will censor deaths. However, a secondary analysis will be conducted in

which death is included as an event in the patency survival curves, to provide re-assurance that death does not modify the outcome of the trial.

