## 7.2 ADVERSE EVENTS

See the study protocol for the definition of adverse events (AE). The investigator's verbatim term for all adverse events will be mapped to System Organ Class (SOC) and preferred terms using the current version of the Medical Dictionary for Regulatory Activities (MedDRA).

From a technical regulatory perspective the HAV is a biologic medicinal product while the ePTFE graft is a device. For the purposes of this study and to allow for better cross-treatment arm comparisons of safety, and given that the IMP is a biologic drug, all events will be reported as if both arms were drugs.

AEs will be summarized as treatment-emergent AEs (TEAEs) for the Safety analysis set.

An AE will be considered a TEAE if the onset of the event is on or after the start of the anesthesia for the implant surgery. If an AE start date is completely missing, then the AE will be considered as TEAE unless it can be determined that the AE end date occurred prior to the anesthesia for the implant surgery. If the AE start date is partially missing then the start date will be imputed as described in Section 4.4.

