### **Adverse Events Summaries**

An overall summary of all TEAEs will be presented overall and by treatment group and will include the following:

- the number and percentage of subjects experiencing a TEAE
- the number and percentage of subjects experiencing a TEAE by strongest relationship to IMP assessed by Principal Investigator and sponsor
- the number and percentage of subjects experiencing a TEAE by strongest relationship to study procedure(s) assessed by Principal Investigator and sponsor
- the number and percentage of subjects experiencing a TEAE by greatest intensity (see Section 9.3 of study protocol for details on intensity)
- the number and percentage of subjects experiencing a TEAE leading to IMP abandonment
- the number and percentage of subjects experiencing a treatment emergent SAE (TESAE)
- Deaths

In the overall summary of TEAEs table, besides tabulating the number and percentage of subjects, the total number of TEAE episodes will also be provided. If a subject has repeated episodes of a particular TEAE, all episodes will be counted in the summary table.

In addition to an overall summary, the following safety data with no inferential statistics will be provided:

- All Treatment Emergent AEs by SOC and PT
- All Serious AEs by SOC and PT
- All Treatment Emergent AEs leading to outcome of death by SOC and PT
- All Treatment Emergent AEs by SOC, PT and greatest severity
- All Treatment Emergent AEs by SOC, PT and greatest causal relationship to IMP and study procedure assessed by Principal Investigator and sponsor

- All Treatment Emergent AEs leading to study discontinuation by SOC and PT

For these summaries, if a subject has repeated events of a particular TEAE, only the most severe event or the event with the strongest causal relationship to IMP will be counted in the summary tables.

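### At the final 60-month analysis, deaths are shown as crude percentages by arm although follow-up after Month 24 depends on patency, so the arm with better patency is expected to show more recorded deaths even when mortality is equal

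*SAP*

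**What the plan says.** **Follow-up.** Under SAP 3.1 each subject is followed until he or she "completes 2 years (24 months) of follow-up after implantation (irrespective of patency status"). The rule then changes: "After 2 years, only subjects with a patent conduit will continue to be followed (while the study conduit remains patent) for up to 5 years". Protocol 4.1 and 4.3 say the same. SAP 4 plans a final analysis once subjects with a patent conduit at Month 24 have reached Month 60 or abandoned the conduit.

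**Counting deaths.** SAP 5.1 lists conduit abandonment and death under this rule: "Frequency counts and percentages of all subjects who are randomized and experience one of the following will be presented for each treatment group". Under SAP 7.2, Adverse Events Summaries, "An overall summary of all TEAEs will be presented overall and by treatment group and will include the following", and the list runs from "the number and percentage of subjects experiencing a TEAE" to a line for deaths. Neither place sets a cut at Month 24, a person-time denominator or a survival estimate for death. We found no provision for vital status once a conduit has been lost after Month 24.

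**Adverse events.** SAP 7.2 defines treatment emergence by a start only: "An AE will be considered a TEAE if the onset of the event is on or after the start of the anesthesia for the implant". The end comes from collection. Under Protocol 9.4, all adverse events are reported to Month 24 or early termination. After that, only HAV-related SAEs and Events of Special Interest are reported.

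**The concern.** After Month 24 the time during which a death can be observed is set by the primary endpoint. A subject who has lost the conduit leaves observation but stays in the denominator. A subject whose conduit lasts remains under observation, and a death is then recorded. If true mortality is the same in both arms, the arm that keeps its conduits longer accumulates more recorded deaths.

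What is at stake is how the final report is read. A mortality percentage by arm is one of the first things a safety reader looks for. Here the difference would mix mortality with patency, and the better the HAV performs, the less favourable its figure is expected to look.

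**Working it through.** **The plan's own figures.** The documents give no expected death percentage. The nearest stated figures with the same patency inputs are the 90% powers in Protocol 10.5 and SAP 11.
- Non-inferiority (60% against 66%): margin hazard ratio ln 0.50/ln 0.60 = 1.357, true hazard ratio ln 0.66/ln 0.60 = 0.813, tested ratio 0.599. With 16 months of accrual plus 12 months of follow-up, and 20% yearly deaths censored, about 158 events are expected and power is 89.5%.
- Superiority (60% against 76%): hazard ratio 0.537, 112 events with 12 months of follow-up for each subject and no losses, power 90.8%.

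Each figure is reproduced under a standard variant, though not under the same one. The patency inputs are therefore usable.

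**Inputs.**
- Mortality: SAP 6.1 describes ESRD patients "with an annual death rate of ~20% (USRDS") and expects similar death rates in the two arms. So d = −ln 0.80 = 0.2231 per year in both.
- 12-month secondary patency s: ePTFE 60%; HAV 66% and 76% (Protocol 10.5); HAV 89%, early Phase 2 data (Protocol 2.4.3.3), here extrapolated to five years. Patency-loss hazard p = −ln s.
- 175 subjects per arm.
- Assumed: constant and independent hazards, no transplant or withdrawal, and every death after Month 24 in a subject with a patent conduit is recorded.

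**Formula.** Recorded deaths by Month 60 = (deaths to Month 24, all subjects) + (alive and patent at Month 24) × (share of these who die while still patent in the next three years)

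= [1 − exp(−2d)] + exp(−2(d+p)) × d/(d+p) × [1 − exp(−3(d+p))]

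The first term is 1 − 0.80² = 36.0% in every arm.

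| 12-month patency | p | Alive and patent at Month 24 | Of these, die while patent by Month 60 | Recorded deaths | Deaths in 175 | Excess over ePTFE |
|---|---|---|---|---|---|---|
| ePTFE 60% | 0.5108 | 0.48² = 23.0% | 0.3040 × 0.8894 = 27.0% | 42.2% | 73.9 | – |
| HAV 66% | 0.4155 | 0.528² = 27.9% | 0.3494 × 0.8528 = 29.8% | 44.3% | 77.5 | 2.1 points |
| HAV 76% | 0.2744 | 0.608² = 37.0% | 0.4485 × 0.7752 = 34.8% | 48.9% | 85.5 | 6.6 points |
| HAV 89% | 0.1165 | 0.712² = 50.7% | 0.6569 × 0.6391 = 42.0% | 57.3% | 100.2 | 15.1 points |

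True five-year mortality is 1 − 0.80⁵ = 67.2% in every row. A simulation of 2 million subjects per scenario agreed with the recorded percentages.

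**Range of the excess (HAV 66%, 76%, 89%).**
- Yearly mortality 10% to 25% (assumption): 1.4 to 2.2, 4.6 to 6.9, and 10.6 to 15.7 points.
- Added withdrawal or transplant of 5% to 15% a year (assumption): 1.2 to 1.8, 3.9 to 5.6, and 8.8 to 12.7 points.
- 24-month analysis with 16-month accrual, if data beyond Month 24 are not cut: 0.6, 1.9 and 4.0 points.
- 18-month analysis on the same basis: 0.3, 0.8 and 1.6 points.
- First 24 months only: zero (36.0%, or 63 of 175, in each arm).

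**Person-time.** Expected person-years of actual follow-up are 331.2, 347.5, 383.1 and 449.2 in the order of the table. Then 73.9/331.2, 77.5/347.5, 85.5/383.1 and 100.2/449.2 all equal 22.3 deaths per 100 person-years, and the artificial difference disappears.

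**The case against.** Five points can be made for the plan.

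1. *No test is planned.* Apart from infections, Protocol 10.4 restricts safety data to description, and SAP 5.1 is a disposition table. This stands. A reader might infer that the trial risks a spurious statistically significant mortality result, but the documents plan no such comparison.
2. *Adverse events are mostly confined to the complete period.* This stands. The open-ended definition of treatment emergence might suggest that all TEAE and serious TEAE percentages are distorted in the same way. Protocol 8.2.6 and 9.4 do not support that: beyond Month 24 only Events of Special Interest and HAV-related SAEs continue. Infections, aneurysms and pseudo-aneurysms also have person-year rates in SAP 7.2.
3. *SAP 6.1 does not rely on the crude table for reassurance about death.* This stands. It relies on a time-to-event analysis with death as an event, repeated in SAP 6.3, which handles follow-up time properly. Those analyses combine death with loss of patency, however, so they do not show mortality itself.
4. *A reader can repair the figure.* This stands in part. There is a separate 24-month analysis, and SAP 7.1 reports subject-years by arm, but nothing links those subject-years to deaths.
5. *Late deaths may not all be recorded.* Protocol 9.4 does not list unrelated SAEs as reportable after Month 24, whereas 9.4.1 requires any SAE during the study to be reported. How many late deaths reach the adverse-event table is therefore unclear. Discontinuation reasons and the rule censoring at death should still identify them in subjects with a patent conduit. This makes the size less certain without removing the mechanism.

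**Conclusion.** The point holds for deaths at the final 60-month analysis. Following SAP 5.1 and the deaths line of SAP 7.2 as written gives a between-arm percentage that is biased against the arm with better patency. Under the stated assumptions the expected HAV excess is about 2 points in the plan's non-inferiority scenario and 7 in its superiority scenario. The 15-point figure rests on extrapolating early Phase 2 patency and is an upper case.

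This is a bias in expectation. A reader might infer that the better arm must show more deaths, but with 175 per arm the chance that HAV shows the higher percentage is 65%, 89% and above 99% in the three scenarios. The bias is small at the 18- and 24-month analyses and absent within the first 24 months. It leaves the primary and key secondary efficacy tests untouched. It is a reporting weakness worth correcting because the correction is cheap.

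**What to change.** - In SAP 5.1 and 7.2, limit by-arm death percentages to Day 0 to Month 24. Do the same for percentages of the event types still collected after Month 24.
- Report later deaths and events in a separate table per 100 person-years of actual follow-up, labelled as subjects with a patent conduit at Month 24. Kaplan-Meier estimates of death, censored at end of follow-up, would also serve.
- Use the subject-years of SAP 7.1, but name loss of patency after Month 24 as an end of follow-up; the present study-period definition names only death and early termination.
- Reconcile Protocol 9.4 and 9.4.1 on whether unrelated deaths after Month 24 are reported.

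The cost is SAP wording and one extra table. The downside is that late deaths leave the headline count and must be read in the second table. HAV-related SAEs after Month 24 have no ePTFE counterpart, so they can be described there but not compared between arms.

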#### **5.2 PROTOCOL DEVIATIONS**

The number and percent of subjects with major protocol deviations will be summarized using the ITT analysis set. See Section 4.2 for more details on protocol deviations.

A by-subject listing will be presented for subjects with major protocol deviations.

### **5.3 DEMOGRAPHIC CHARACTERISTICS**

All demographic characteristics including gender, age (years), race/ethnicity, weight (kg), height (cm), etc. will be summarized using the ITT analysis set for each treatment group as well as for all subjects. Body mass index (BMI) will be calculated from available data:

$$\text{BMI} = [\text{Weight (kg)}] / [\text{Height (m}^2\text{)}]$$

Categorical variables will be summarized using frequencies and percentages and continuous measures will be summarized using the number of non-missing observations, mean, standard deviation, median, first and third quartiles, minimum and maximum. No formal hypothesis testing will be performed to compare differences in demographic characteristics between treatment groups. A by-subject demographic listing will be provided.

### **5.4 BASELINE CHARACTERISTICS**

Baseline characteristics, including duration of end-stage renal disease, number of previous conduits placed with a description of what they were, etc. will be summarized using the ITT analysis set for each treatment group as well as for all subjects. Categorical variables will be summarized using frequencies and percentages and continuous measures will be summarized using the number of non-missing observations, mean, standard deviation, and possibly other descriptive statistics. No formal hypothesis testing will be performed to compare differences in baseline characteristics between treatment groups. A by-subject baseline characteristics listing will be provided.

### **5.5 MEDICAL HISTORY**

A detailed medical history for each subject including the cause(s) of renal failure, history of dialysis and past vascular access procedures and smoking history will be obtained during screening. The number and percent of subjects with previous and active medical history at screening will be summarized and presented by body system using the ITT analysis set for each treatment group. A by-subject listing will also be created.

### **5.6 PRIOR AND CONCOMITANT MEDICATIONS**

Prior medications are defined as all prescription medications plus aspirin taken within 7 days (whether continuing or not) prior to surgery (Day 0). Concomitant medications are defined as all prescription medications and aspirin taken at any time from Day 0 through the Month 24 visit. All prior and concomitant medications (including immediately pre-surgery and post-surgery medications) must be listed in the subject's medical record and recorded in the eCRF. Medications

used during anesthesia should be recorded in the anesthesia records but should not be transcribed in the eCRF. Medications used during anesthesia will not be included in any listings.

Prior and concomitant medications will be classified according to the most recent World Health Organization (WHO) drug dictionary available at the time of analysis. Prior and concomitant medications will be summarized using frequency and percentage by default Anatomical, Therapeutic, and Chemical (ATC) class, Preferred Term (PT) and treatment group using the ITT analysis set.

All concomitant medication data will be listed, sorted by treatment group, subject number, start and stop date. For antibiotics, the listing will also include medication generic name/components of combination product, indication, dose, frequency and route of administration.

## 6 EFFICACY ANALYSIS

### 6.1 PRIMARY EFFICACY ENDPOINT AND ANALYSIS

The primary efficacy endpoint is the time to loss of Secondary Patency assessed when all patients are at least 18 months after implantation (or have been censored). The primary analysis will be non-inferiority analysis using the following censoring rules:

- Subjects who have patent study conduits at the time of death, kidney transplant, voluntary withdrawal will be censored at that timepoint
- Subjects who are lost to follow-up will be censored at their last visit when it was known that the study conduit was patent
- Subjects who are lost to follow up and whose study conduit was not patent at the last completed visit will be treated as abandoned at the time of study conduit occlusion
- Subjects in whom a delayed decision is made to abandon the study conduit (e.g. delayed and then failed thrombectomy) will have the date of abandonment set as the date of the initial recognition of the thrombosis, not the date that a final decision is made
- For subjects who discontinue early or who complete without meeting criteria for the event, the time-to-event will be censored and defined as the number of days from randomization to the subject's last visit during the study

These censoring rules will apply to all 'time to' analyses. Subjects with End Stage Renal Disease (ESRD) have significant co-morbidities, with an annual death rate of ~20% (USRDS). Given the nature of the investigational product and the clinical setting, it is unlikely that the investigational product will be a causative factor in the overall death rate, and it is likely that the non-product related death rate will be similar in the two arms. For this reason, the primary analysis of Primary and Secondary Patency will censor deaths. However, a secondary analysis will be conducted in

which death is included as an event in the patency survival curves, to provide re-assurance that death does not modify the outcome of the trial.

The hazard ratio (HAV relative to ePTFE graft) will be estimated using a Cox proportional hazards regression with treatment group and the surgical placement stratification variable as factors. Based on the estimated event-free rate in the ePTFE graft arm at the data cut-off using Kaplan-Meier method, the non-inferiority margin will be determined by the hazard ratio corresponding to a difference of 10 percentage points. Hazard Ratio (HAV to ePTFE) Margin = $\text{Log}(\text{ePTFE K-M estimated event free rate} - 0.1) / \text{Log}(\text{ePTFE K-M estimated event free rate})$ . For analyses conducted at 12 months, the hazard ratio will be calculated from the ePTFE K-M estimated event-free rate at 12 months. For analyses conducted at 18 months, the hazard ratio will be calculated from the ePTFE K-M estimated event-free rate at 18 months. Similarly, for analyses conducted at 24 months, the hazard ratio will be calculated from the ePTFE K-M estimated event-free rate at 24 months. If the upper limit of the two-sided 95% confidence interval for the hazard ratio is less than the corresponding non-inferiority margin hazard ratio, then non-inferiority will be demonstrated.

The primary analysis will be in the ITT analysis set. The analysis of the primary endpoints of interest will be repeated using the mITT and per-protocol analyses sets as confirmatory.

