10.3 Efficacy Analysis

10.3.1 Censoring for Time to Event Analyses

- Subjects who have patent study conduits at the time of death, kidney transplant or withdrawal will be censored at that timepoint (additional efficacy analyses will consider death as an event-see [Section 10.3.4](#)).
- Subjects who are lost to follow-up will be censored at their last visit when it was known that the study conduit was patent.
- Subjects in whom a delayed decision is made to abandon the study conduit (e.g., delayed and then failed thrombectomy) will have the date of abandonment set as the date of the initial recognition of the thrombosis, not the date that a final decision was made.

These censoring rules will apply to all 'time to' analyses.

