## 6.2 SECONDARY EFFICACY ENDPOINTS AND ANALYSES

If the primary efficacy analysis demonstrates non-inferiority, the following key secondary efficacy analyses will be performed at the same timepoint in the ITT analysis set using a fixed sequence testing procedure to control the overall level of significance. Thus, the results of a given key secondary analysis will be considered confirmatory only if the results of all previous tests are successful based on the use of a two-sided test at the alpha=0.05 level of significance. However, once a non-successful result is obtained, all subsequent results will be considered as exploratory rather than confirmatory. The key secondary analyses are the following:

- Superiority analysis of the time to loss of Secondary Patency using the same statistical approach as specified for the primary analysis, except that a two-sided superiority test will be performed,
- Non-inferiority analysis of the time to loss of Primary Patency using the same statistical approach and non-inferiority margin as specified for the primary analysis, and
- Superiority analysis of the time to loss of Primary Patency using the same statistical approach as specified for the primary analysis, except that a two-sided superiority test will be performed.

In order to provide descriptive summary statistics that are of interest, point estimates and 95% confidence intervals for patency (Primary, Primary Assisted and Secondary) survival probabilities will be provided for each group at 6, 12, 18, and 24 months. These estimates will be computed from Kaplan-Meier survival curves for each treatment group for each of the endpoints. For subjects who discontinue early or who complete without meeting criteria for the event, the time-to-event will be censored and defined as the number of days from randomization to the subject's last visit during the study.

Other secondary endpoints to be analyzed include:

- Interventions required that successfully achieved/maintained Secondary Patency. Interventions include whatever is done at one session. For example, thrombectomy + angioplasty at one session would be considered as 1 intervention. Summaries will include:
  - Proportion of subjects who had at least one intervention
  - Number of interventions per subject
  - Distribution of how many had 1, 2, 3... interventions

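### The SAP gives two overlapping censoring rules with no precedence; censoring at the last visit while events keep their own date lowers the reported patency rates and departs from the protocol

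*SAP*

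**What the plan says.** Protocol 10.3.1 sets the rule for all time-to-event analyses: "Subjects who have patent study conduits at the time of death, kidney transplant or withdrawal will be censored at that timepoint". It uses a visit date in one case only: "Subjects who are lost to follow-up will be censored at their last visit when it was known that the study conduit was patent". SAP 4.4 does the same.

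SAP 6.1 opens its list in line with the protocol: "Subjects who have patent study conduits at the time of death, kidney transplant, voluntary withdrawal will be censored at that timepoint". The last bullet of that list adds a second rule. It begins "For subjects who discontinue early or who complete without meeting criteria for the event" and sets the censoring time to "the number of days from randomization to the subject's last visit during the study". SAP 6.1.1 carries the same pair for the 24-month analysis. SAP 6.2 states only the second rule, directly after announcing Kaplan-Meier patency rates at 6, 12, 18 and 24 months: "the time-to-event will be censored and defined as the number of days from randomization to the subject's last visit during the study".

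Events are not moved to visits. For a delayed decision to abandon, SAP 6.1 says the subject "will have the date of abandonment set as the date of the initial recognition of the thrombosis". Protocol 8.5.1 spaces visits six months apart after Month 12, with windows of one month either way from Month 9.

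**The concern.** A subject who dies or withdraws with a patent conduit can fall under both bullets, and nothing says which prevails. Two programmers could derive different censoring dates for the primary endpoint from the same text.

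The two dates also give different estimates. Take two subjects last seen at Month 12. One abandons the conduit at Month 17 and counts as an event at Month 17. The other dies at Month 17 with a patent conduit and, under the last-visit rule, leaves the risk set at Month 12. The five event-free months are lost, while the event in the same interval is kept. The risk set is too small between visits, so Kaplan-Meier patency is too low. What is at stake is the accuracy of the absolute patency rates and agreement with the protocol. The 18-month ePTFE rate also enters the margin formula, so that effect needs checking.

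**Working it through.** **Inputs from the documents.** ePTFE patency 60% and HAV 66% at 12 months; 1:1 allocation; 350 subjects; 16 months' accrual (SAP 11). Deaths about 20% per year; 10-point margin converted to a hazard ratio (SAP 6.1). Visit times and windows (Protocol 8.3 to 8.6).

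**Assumptions not in the documents.** Exponential failure times, independent censoring, visit dates uniform within windows, and a data cut 19 to 35 months after implantation for the 18-month analysis. Withdrawal or transplant is zero in the base case and varied below. Subjects still followed at the cut are taken to fall under the last-visit rule, because the SAP gives no data cut-off rule for them.

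**The plan's own figure first.** The documents quantify power but not the censoring effect. HR under the alternative = ln 0.66 / ln 0.60 = 0.813; margin HR = ln 0.50 / ln 0.60 = 1.357. With 20% annual deaths and 12 months' follow-up after accrual, 157.9 events are expected. Then z = ln(1.357/0.813) × √157.9 / 2 − 1.96 ≈ 1.25, which is power of 89.5% against the stated 90%. The inputs are therefore a fair base.

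**True ePTFE rates.** 0.60^1.5 = 46.5% at 18 months; 0.60^2 = 36.0% at 24 months.

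**Simulated ePTFE Kaplan-Meier rates** (large samples, exact event dates, 20% annual deaths; differences from unrounded values):

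| Rate and data cut | Date of death or cut-off | Last visit only for those still followed | Last visit for all event-free |
|---|---|---|---|
| 18 months, 18-month cut | 46.4% | 46.3% (−0.1) | 45.1% (−1.4) |
| 24 months, 18-month cut | 36.0% | 33.8% (−2.2) | 32.3% (−3.7) |
| 24 months, scheduled 24-month analysis | 36.0% | 35.9% (−0.1) | 34.5% (−1.5) |

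The middle column at the 18-month cut ranges from −2.1 to −2.3 for the 24-month rate as other losses and deaths vary. With last visit for all, the 6- and 12-month rates fall by 0.4 and 0.8 points.

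**Sensitivity, last visit for all, 18-month cut.**
- 10% deaths only: −0.7 at 18 months, −2.9 at 24.
- 20% deaths plus 10% other loss, no termination visit: −1.9 and −4.3.
- The same, with a termination visit at every withdrawal: −1.3 and −3.6.
- 20% deaths plus 20% other loss, no termination visit: −2.6 and −5.1.
- Early-weighted failure (Weibull shape 0.7), same range of losses: −0.6 to −2.2 at 18 months.

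**Effect on the comparison.** The HAV arm shifts almost equally (53.5% to 52.2% at 18 months). The hazard ratio is 0.815 against 0.817. The margin is ln(0.3644)/ln(0.4644) = 1.316 against ln(0.3509)/ln(0.4509) = 1.315. In 3,000 simulated trials of 175 per arm, non-inferiority succeeded in 88.6% against 88.2% at the design alternative, and in 2.2% against 2.3% at the margin.

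**The case against.** The strongest reply is that the specific bullet naturally governs death, transplant and voluntary withdrawal, and the last-visit bullet is residual. SAP 6.1 says its censoring rules cover every time-to-event analysis, so 6.2 need not displace them. For withdrawals, Protocol 8.7 seeks an early termination visit, which often makes the two dates equal. The rates concerned are described in SAP 6.2 as descriptive.

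Much of this stands. On that reading the understatement is about 0.1 points both at 18 months and at the scheduled 24-month analysis. It does not dispose of the point: the SAP never states that precedence, 6.2 names only the last-visit rule, a termination visit cannot help for deaths, and about 2 points remain for the 24-month rate read from the 18-month cut. SAP 6.2 does call for that rate, and it places the secondary analyses after 18 months.

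Two stronger inferences are tempting and should not be drawn. One is that the planned 24-month result is understated by nearly 4 points. That figure needs last-visit censoring even for deaths, together with an immature cut. SAP 1, 4 and 6.1.1 schedule a separate 24-month analysis, where the most is 1.5 points with deaths as the only loss. The other is that the non-inferiority conclusion is at risk because the ePTFE rate feeds the margin. The figures show no practical change, because both arms shift alike.

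It is also fair to say that censoring everyone at the cut-off is not safe on its own. Patency is assessed at visits, and assuming it to the cut-off would bias rates upward if recent abandonments are not yet reported.

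**Conclusion.** The rule is wrong as written: two overlapping instructions without precedence, one of which conflicts with Protocol 10.3.1 and SAP 4.4 and lowers the Kaplan-Meier patency rates. The lower end of each range quoted in the summary applies if the specific bullet governs deaths and withdrawals, and the upper end if the last visit is used for everyone. These sizes rest on exponential failure and 20% annual deaths. Withdrawals without a termination visit would add to them, and a lower death rate would reduce them. The effect is confined to the reported absolute rates and to consistency with the protocol. The conclusion on the hazard ratio and margin assumes that loss is similar in the two arms; if deaths or withdrawals differed by arm, it would need to be rechecked. Last-visit censoring for loss to follow-up is the protocol's own rule and is not at issue.

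**What to change.** Put one rule with explicit precedence in SAP 6.1, 6.1.1 and 6.2:

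1. Patent at death, transplant or withdrawal: censor on that date.
2. Lost to follow-up: censor at the last visit with known patency.
3. Still followed: censor at the data cut-off if the conduit is confirmed in use to that date. Otherwise censor at the last date of confirmed patency, and count events only up to that same date.

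Either omit the 24-month rate from the 18-month analysis or label it provisional.

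The cost is SAP wording, plus a small amount of work to confirm conduit status at the cut-off. The fallback in rule 3 discards a few late events but treats events and event-free time alike. Under the base assumptions the first rule and a confirmed cut-off return 46.4% at 18 months and 36.0% at 24 months, in line with the true 46.5% and 36.0%.
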